8.4.3.3 Expectedness

Clinical research staff will be responsible for determining whether an adverse event (AE) is expected or unexpected. An AE will be considered unexpected if the nature, severity, or frequency of the event is not consistent with the risk information previously described for the study intervention.

8.4.4 Time Period and Frequency for Event Assessment and Follow-Up

The occurrence of an adverse event (AE) or serious adverse event (SAE) may come to the attention of study personnel during study visits and interviews of a study participant presenting for medical care, or upon review by a study monitor.

All AEs including local and systemic reactions not meeting the criteria for SAEs will be captured on the appropriate case report form (CRF). Information to be collected includes event description, time of onset, clinician's assessment of severity, relationship to study intervention (assessed only by those with the training and authority to make a diagnosis), and time of resolution/stabilization of the event. All AEs occurring while on study must be documented appropriately regardless of relationship. All AEs will be followed to adequate resolution.

Any medical condition that is present at the time that the participant is screened will be considered as baseline and not reported as an AE. However, if the study participant's condition deteriorates at any time during the study, it will be recorded as an AE.

Changes in the severity of an AE will be documented to allow an assessment of the duration of the event at each level of severity to be performed. AEs characterized as intermittent require documentation of onset and duration of each episode.

Clinical research staff will record all reportable events with start dates occurring any time after informed consent is obtained until 7 (for non-serious AEs) or 14 days (for SAEs) after the last day of study participation. At each study visit, the investigator will inquire about the occurrence of AE/SAEs since the last visit. Events will be followed for outcome information until resolution or stabilization.

All serious adverse events (SAEs) will be followed until satisfactory resolution or until the PI deems the event to be chronic or the participant is stable.

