- All participants will perform the CPET with 12-lead ECG at the CC that is monitored by credentialed RMD staff members experienced with clinical exercise testing
- Gradual exercise progression with supervision by RMD staff members specifically credentialed for the supervision of aerobic exercise in clinical populations
- Thrice weekly check-ins to include monitoring of vital signs and symptoms before and after exercise during the 10 week AET intervention

Considerable overlap has been observed between the constellation of persisting symptoms in the post COVID-19 condition and ME/CFS (53). Featured among them is PEM, which was self-reported in 59% of surveyed participants reporting sequelae post COVID-19 (30). The distinguishing nature of PEM is the wide variety of worsening symptoms that may occur among individuals (from physical/mental fatigue to cold-like symptoms) and the onset or duration of symptoms (from hour to days) (54). Triggers of PEM not only include physical activity, but also mental effort and emotional stressors (54). It was recently observed that individuals identified as having PEM and post-acute sequelae of SARS-CoV2 (PASC) showed a multitude of abnormalities following a CPET, compared to a control group of individuals that had no lingering symptoms post COVID-19 (48). These abnormalities included compositional changes in skeletal muscle fibers, metabolic dysfunction, and muscle tissue damage in samples taken the day after the CPET (48). However, repeated muscle biopsies may have affected some of these findings, as the control group also showed these changes and interactions for group and time were not significant. Further, the PASC group averaged 17.9 months since initial infection, which was almost 4 times longer than the control group at 4.7 months. This extended duration of living with PASC may also account for some of the observed differences.

Specifically for PASC patients experiencing PEM, exercise recommendations “...*should follow a slow, progressive approach and be regularly evaluated in regard to symptom severity and the health status of patients*” (55). The following considerations are in place to minimize risk for patients that have or develop PEM during the study:

- Screening prior to enrollment to exclude potential participants that are identified as having PEM
- Perform assessment of PEM during H&Ps, and as needed throughout the study, by NIH medical staff for management of participants.

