5.6.2 Compensation

- There is no compensation for participants that perform the COVID-19 antibody testing only.
- Participants will receive compensation for research activities and interventions, based on research-related inconveniences and time. Participants may receive up to the following amounts, depending on the study arm, assessments performed and optional procedures completed:

	AET+	CON
Study Visit 1 (+ optional measures)	\$ 880 (+\$ 90)	\$ 880 (+\$ 90)
Study Visit 2 (+ optional measures)	\$ 860 (+\$ 40)	\$ 860 (+\$ 40)
Study Visit 3 (+ optional measures)	N/A	\$ 780 (+\$ 40)
30 Exercise Training Visits at \$30/session	\$ 900	\$ 900
10 Education sessions at \$10/session	\$ 100	\$ 100
Four 3-month follow-ups (\$60/follow-up)	\$ 240	\$ 240
MAX TOTAL (+ OPTIONS)	\$ 2980 (+\$ 130)	\$ 3840 (+\$ 170)

- Payment will be processed after completion of the study visits and each 3-month follow-up period
- Should participants be unable to finish the study, they will be paid for parts completed
- No travel reimbursement will be provided
- For NIH staff participants, please refer to NIH HRPP Policy 404

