6.1.1.1 Educational Sessions

The education portion will comprise of 10 separate weekly lectures, lasting approximately 1 hour. Sessions will be conducted by credentialed RMD staff members and participants in both the CON and AET+ arm will receive the same educational lectures remotely within the 10-week intervention period. Educational topics to be covered will be related to exercise programming, safety and well-being such as considerations for benefits and adaptations of exercise, relevant anatomy and physiology, nutrition and lifestyle considerations, managing co-morbid conditions, forms of exercise training, home recommendations, and locating community resources.

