6.1.1.2 Aerobic Exercise Training Sessions

The AET regimen will consist of 10 weeks of aerobic exercise. Vital signs and review of cardiac-related signs or emerging symptoms will be performed before and after every session. Following a brief warm-up period, participants will be encouraged to target 30 minutes of aerobic exercise, followed by a brief cool-down. The sessions will be continuous unless the participant cannot tolerate the regimen, in which case the exercise bouts will be alternated with rest intervals until the total time of the exercise bouts equals the 30 minutes. The intensity of exercise will be guided using heart rate (HR), and gradually increased from light-moderate to moderate-high intensity as safely tolerated by the participant.

The frequency of the sessions will be 3 times per week, unless make up sessions are needed in the 10 weeks. The target endpoint for each session will be completion of the prescribed training time, however symptomatic endpoints for stopping the training session will be those recommended by the ACSM, or as needed for the safe management of participants.

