8.3 SAFETY AND RESEARCH ASSESSMENTS

The following assessments are performed for research purposes and will be conducted at all study visits to the NIH (i.e., study visit 1, 2 and 3), unless specified otherwise or performed recently at the NIH. Assessments performed for safety (i.e., vital signs and review of signs/symptoms) will be performed as described. It is anticipated that participants in this study may not complete the entire list of assessments (e.g., questionnaires, vascular tests, etc.).

Omissions such as these will be considered expected provided they are not the primary outcome, not related to determination of the exercise training range and do not include data needed to assess safety for a procedure.

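### Up to Visit 2, symptoms are reviewed far more often in AET+ than in CON, and no common method of asking about adverse events is described, so by-arm counts would partly reflect contact frequency.

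*Combined protocol and SAP*

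**What the plan says.** **Active inquiry.** Section 8.4.4: "At each study visit, the investigator will inquire about the occurrence of AE/SAEs since the last visit". Section 8.3 uses the term for the on-site assessments: "study visits to the NIH (i.e., study visit 1, 2 and 3". Section 8.4.4 also lists participants presenting for medical care and review by a study monitor as ways an event may come to light. It requires all on-study events to be documented. The recording window closes 7 days (non-serious) or 14 days (serious) after participation ends.

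**AET+ in the randomised period.** Section 6.1.1.2: "Vital signs and review of cardiac-related signs or emerging symptoms will be performed before and after every session". Section 2.3.3 lists as a risk-reduction measure: "Thrice weekly check-ins to include monitoring of vital signs and symptoms before and after exercise during the 10 week AET intervention". Section 2.3.1.15 adds pain assessment around each session and a check on how the previous session was tolerated.

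**CON in the randomised period.** Section 6.1.1.1 says "participants in both the CON and AET+ arm will receive the same educational lectures remotely within the 10-week intervention period". It describes no symptom or adverse event question at these sessions. The SOA marks vital signs in Intervention Period 1 for AET+ but not for CON.

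**Schedule of Activities.** In both arms the adverse event review row runs as a line from Intervention Period 1 to the fourth 3-month follow-up (week 69 in AET+, week 84 in CON). Sections 8.3.6 and 8.3.9 describe those follow-ups as digital or paper questionnaires and a mailed activity monitor.

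**Analysis.** Section 9.4.4 marks safety analyses as not applicable.

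**The concern.** The two arms differ in how hard events are looked for, as well as in exercise. Aches, dizziness and fatigue flares in AET+ would come up within days. In CON, on the procedure described, they must be recalled at Visit 2. Section 8.4.4 asks for onset and duration of each episode of an intermittent event, and a participant is unlikely to reconstruct those after about three months.

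This matters more here than in most exercise trials. Section 2.3.1.8 treats the effect of exercise on post-exertional malaise as an open question. Section 4.2 justifies the control arm by how little is known about spontaneous recovery. Background flares in CON are thus the yardstick for judging harm from exercise, and they are the events least actively sought. Section 10.10.1 commits the trial to posting results on ClinicalTrials.gov, where by-arm counts may be read as a comparison. No planned safety analysis exists to qualify them.

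**Working it through.** **1. Contact count, randomised period.** Section 6.1.1.2: "The frequency of the sessions will be 3 times per week, unless make up sessions are needed in the 10 weeks". So 3 per week × 10 weeks = 30 sessions, which reproduces the compensation table in Section 5.6.2 ("30 Exercise Training Visits"). With a review before and after each, 30 × 2 = 60. Under the 80% attendance rule in Sections 7.1 and 9.3, a retained AET+ participant has at least 0.80 × 30 = 24 sessions, or 48 reviews.

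| Up to Visit 2 | AET+ | CON |
|---|---|---|
| Weekly education contacts | 10 | 10 |
| Exercise sessions | 24 to 30 | 0 |
| Session symptom reviews described | 48 to 60 | 0 |
| Stated active inquiry covering the period | Visit 2 | Visit 2 |

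**2. Recall interval.** In AET+, three sessions a week are on average 7 / 3 = 2.3 days apart. In CON, Visit 1 (week 1) to Visit 2 (week 14) is 14 − 1 = 13 weeks. The Visit 2 window of ±4 weeks alone gives 10 − 1 = 9 to 18 − 1 = 17 weeks. Adding Visit 1's ±2 weeks gives 10 − 3 = 7 to 18 − (−1) = 19. The low ends are shorter than the 10-week intervention, so they cannot apply to anyone who completes it.

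**3. After the last study visit.** The SOA review line runs 69 − 14 = 55 weeks in AET+ and 84 − 29 = 55 weeks in CON. The first follow-up contact comes 30 − 14 = 16 and 45 − 29 = 16 weeks after the last visit. Both arms are alike here. The gap is that no adverse event inquiry is described at these contacts. The fatigue-symptom scale used to capture post-exertional malaise (Section 8.3.6.6) is not given during this year.

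**4. Section 8.4.4 against the SOA.** The text places inquiry at study visits, while the SOA shows review throughout. A line on a schedule does not say who asks, what, or how often.

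**5. Illustration of the consequence.** These assumptions are not in the documents: equal true risk in both arms, full capture in AET+, and a fraction r of CON events recalled at Visit 2. The apparent AET+:CON ratio is then 1/r. Taking a true risk of 30% and the plan's 38 completers per arm, expected participants with an event are 38 × 0.30 = 11.4 in AET+ and 11.4 × r in CON.

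| r | Apparent ratio | AET+ | CON |
|---|---|---|---|
| 0.5 | 2.00 | 11.4 | 5.7 |
| 0.7 | 1.43 | 11.4 | 8.0 |
| 0.9 | 1.11 | 11.4 | 10.3 |
| 1.0 | 1.00 | 11.4 | 11.4 |

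The documents give no value for r, so the table shows only how the artefact would behave.

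**The case against.** A reader might infer that CON is asked about events only at study visits, that nobody is asked after the last visit, and that late events are lost. The documents do not support any of these. The SOA carries adverse event review in both arms from Intervention Period 1 to the final follow-up. What is missing is a described method of asking. Late events also have other routes: presentation for care, monitor review, and follow-up questionnaires, two of which (Sections 8.3.6.7 and 8.3.6.8) trigger assessment when scores are high. The recording window outlasts participation.

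Nor are CON's symptoms unobserved. Both arms complete the same questionnaires at Visits 1 and 2, with the fatigue-symptom scale repeated up to seven times around the exercise test. Sections 2.3.1.8 and 2.3.3 provide for watching for post-exertional malaise during the study without limiting this to AET+.

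The figure of 60 against 0 also needs care. Session reviews are exercise-safety checks, not formal adverse event inquiries, so it measures opportunity for detection. Extra contact in a supervised-exercise arm is partly unavoidable, CON receives the same checks after crossover, and no between-arm safety test is planned.

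All of this stands as a limit on how strongly the point can be put. It does not supply a common question, and questionnaire scores do not replace asking what happened and when.

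**Conclusion.** The narrower point holds. Up to Visit 2, described symptom contact is much denser in AET+ (up to 60 session reviews, against none described for CON between visits), and the only stated active inquiry for CON looks back about 13 weeks. By-arm counts collected as written would partly reflect contact frequency. It would go too far to call them biased by a known amount, because that depends on CON recall and on what staff actually ask, and the documents give neither. For the 55 weeks after the last study visit, capture is mainly passive in both arms, and Section 8.4.4 and the SOA must be reconciled.

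The conclusion assumes that no separate manual or CRF guideline already specifies a common question; none is described. The primary 6MWT comparison is not affected. This is a cheap improvement to how safety information is collected and reported.

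**What to change.** 1. Reconcile Section 8.4.4 with the SOA, stating who asks, how, and at which contacts.
2. Ask one short, identically worded adverse event question in both arms at each of the ten weekly education contacts, and again at each 3-month follow-up. The electronic self-report module in Section 10.8.1 could carry it.
3. Add a field to the adverse event CRF for how the event was detected: common question, exercise-session check, study visit, or other.
4. Base any between-arm summary up to Visit 2 on the common question plus the Visit 2 inquiry. List session-detected events separately.

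**Cost.** No extra visits are needed, but there is extra work. For 76 to 90 participants, ten weekly forms make 10 × 76 = 760 to 10 × 90 = 900, and four follow-up forms make 4 × 76 = 304 to 4 × 90 = 360. More minor events will be recorded, and Section 8.4.4 requires each to be assessed for severity and relatedness and followed to resolution. Repeated prompting carries a small risk of influencing self-reported outcomes, though it would be applied equally in both arms.

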8.4.5 Adverse Event and Serious Adverse Event Reporting

Reporting of AEs and SAEs that do not meet the definition of an Unanticipated Problem (UP) will be reported at the time of Continuing Review (CR) to the NIH IRB as specified in NIH HRPP SOP Policy 801.

Death of a research participant that is possibly, probably or definitely related to the research must be reported within 24 hours of the investigator becoming aware of the death to NIH IRB.

8.5 UNANTICIPATED PROBLEMS

Unanticipated problems (UPs) are defined as described in NIH HRPP SOP Policy 801.

8.5.1 Definition of Unanticipated Problems (UP)

Any incident, experience, or outcome that meets all of the following criteria:

- Unexpected (in terms of nature, severity, or frequency) given (a) the research procedures that are described in the protocol-related documents, such as the IRB-approved research protocol and informed consent document; and (b) the characteristics of the participant population being studied; and

- Related or possibly related to participation in the research (“possibly related” means there is a reasonable possibility that the incident, experience, or outcome may have been caused by the procedures involved in the research); and
- Suggests that the research places participants or others (which many include research staff, family members or other individuals not directly participating in the research) at a greater risk of harm (including physical, psychological, economic, or social harm) related to the research than was previously known or expected.

8.5.2 Unanticipated Problem (UP) Reporting

The NIH PI/designee will report unanticipated problems (UPs) to the NIH IRB as per Policy 801. A UP must be reported within 7 calendar days of an investigator becoming aware of the actual or suspected UP. Reporting of UPs will also be reported at the time of Continuing Review (CR) to the NIH IRB as specified in NIH HRPP SOP Policy 801.

8.6 NON-SIGNIFICANT RISK (NSR) DEVICE STUDY

We believe this study is a non-significant risk (NSR) device study subject to the abbreviated IDE requirements of 21 CFR 812.2(b). The device, as used in this study, does not meet the definition of a significant risk (SR) device per 21 CFR 812.3(m) because:

- (1) it is not intended as an implant and does not present a potential for serious risk to the health, safety, or welfare of a subject;
- (2) it will not be used in supporting or sustaining human life, and does not present a potential for serious risk to the health, safety, or welfare of a subject;
- (3) it will not be used of substantial importance in diagnosing, curing, mitigating, or treating disease, or otherwise preventing impairment of human health and does not present a potential for serious risk to the health, safety, or welfare of a subject because the Magnetic Resonance in research mode operates below the limits that the FDA deems to present significant risk as defined in the FDA guidance document, Criteria for Significant Risk Investigations of Magnetic Resonance Diagnostic Devices; and
- (4) it does not otherwise present a potential for serious risk to the health, safety, or welfare of a subject because the Magnetic Resonance in research mode operates below the limits that the FDA deems to present significant risk as defined in the FDA guidance document, Criteria for Significant Risk Investigations of Magnetic Resonance Diagnostic Devices.

Per regulations, abbreviated IDEs (NSR device studies) do not require an application to the FDA as the IRB acts as FDA’s surrogate for review, approval, and continuing review of these type of device studies.

8.6.1 Sponsor Reporting for NSR Device Study

The PI will report all unanticipated adverse device effects (UADEs) to the Sponsor within 10 working days. This should be submitted to the ORSC RSS by a MedWatch Form (Form 3500A), which should be sent ENCRYPTED to the [contact] inbox with a cc to the CD/CMO/designee. The Sponsor will immediately conduct an evaluation, with the PI, to determine if the UADE presents unreasonable risk to subjects. If the Sponsor determines that the UADE presents unreasonable risk, part of the study presenting the risk or all of the study will be

terminated within 5 working days of the determination, and no later than 15 working days after the Sponsor received notice of the UADE. For non-significant risk device investigations terminated due to an UADE, a sponsor may not resume a terminated investigation without IRB and FDA approval.

All AEs will be sent to the Sponsor quarterly, or at minimum annually. For non-significant risk device studies, this information should be included in the continuing review to the IRB.

In addition, the PI will report to the Sponsor, within 5 working days, a withdrawal of approval by the reviewing IRB of the investigator's part of an investigation. The Sponsor will notify the FDA of withdrawal of IRB approval.

The PI will report to the Sponsor, within 5 working days, if the device is used without obtaining informed consent. The Sponsor will notify the FDA of use of the device without informed consent.

The PI will report to the Sponsor any request to return, repair, or otherwise dispose of any units of a device. The Sponsor will notify the FDA within 30 working days.

9 STATISTICAL CONSIDERATIONS

9.1 STATISTICAL HYPOTHESIS

- Primary endpoints

For Objective #1, we will test the hypothesis that AET will improve physical function, as measured by the 6MWT distance. The 6MWT distance is the primary outcome variable for this RCT and thus our project is powered on the sample size estimated to achieve a significant change in this outcome (See Sample Size section below). Outcome variables will be measured at baseline (study visit 1) and following the 10-week intervention (study visit 2).

- Secondary Endpoints

For Objective #2, we will test the hypothesis that AET will improve patient reported outcomes and other health-related QoL components. For Objective #3, we will test the hypothesis that AET will improve free-living physical activity and sleep quality. All outcome variables will be measured at baseline (study visit 1) and following the 10-week intervention (study visit 2).

9.2 SAMPLE SIZE DETERMINATION

The sample size is calculated based on the primary outcome of 6MWT distance. Based on findings from an RCT of similar exercise interventions in participants recovering from SARS (26), the mean improvement of the 6MWT distance in the AET+ group over the CON group is expected to be 56.7 meters ($20.7 \pm \text{SD}=98.6$ meters for the control group and $77.4 \pm \text{SD}=71.3$ meters for the exercise group). With a significance level of 0.05, 80% power and 1:1 randomization to two groups, a sample size of 38 in each group is adequate to detect such a difference. Sample size was determined by the Power Analysis and Sample Size (PASS) program for a two-sample t-test with unequal variance.

Our recruitment goal was therefore set at 76 participants, however, 85% of randomized participants are expected to complete at least the second study visit. Therefore, 90 participants

need to be randomized in order to achieve 76 completed participants. Recruitment will remain open until 38 participants in each of the AET+ and CON cohorts have completed at least the second study visit (i.e., 10-week time point).

It is expected that approximately 4 to 8 participants will be enrolled each month, such that target enrollment may be reached within 1.5 to 2 years.

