- Secondary Endpoints: Patient-reported outcomes and other health-related components after 10 weeks post-randomization with AET+ and CON; Free-living physical activity and sleep quality after 10 weeks post-randomization with AET+ and CON.
- Exploratory Endpoints: Clinical outcomes, cardiorespiratory function, cognition, biomarkers, metabolomics, ultrasound-based muscle measurements, and vascular function after 10 weeks post-randomization with AET+ and CON; Collection of initial feasibility data to conduct exercise sessions remotely; Explore relationships between the physiological variables and post-study health outcome variables over time.

Abbreviated Title: Exercise and COVID-19**Version Date: 3/18/2025**

Study Population: Ninety male and female adults (18 to 80 years old) recovering from COVID-19, from the greater Washington DC metropolitan area.

Phase: N/A

Description of Sites/Facilities Single-site study (NIH Clinical Center)

Enrolling Participants:

[figure not shown]
Description of Study Intervention: Aerobic Exercise Training: Participants will perform aerobic exercise, 3 times a week for 10 weeks, with supervision by credentialed RMD staff members. Participants will be encouraged to target 30 minutes of continuous aerobic exercise. The intensity of exercise will be gradually increased from light-moderate to moderate-high as safely tolerated by the participant and guided using heart rate targets.
Education: Participants will have weekly education sessions for 10 weeks. All sessions are ~1 hour and will be conducted remotely by credentialed RMD staff members.

Participants randomized to AET+ will perform both exercise training and education during the 10 week intervention period. Participants randomized to CON will perform education only during the first 10 weeks, followed by exercise training during the second 10 weeks (crossover).

Study Duration: 36 months

Participant Duration: Up to 17 months if randomized to AET+, and up to 21 months if randomized to CON

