1.3 SCHEDULE OF ACTIVITIES (SOA)

Procedures	Screening Phase - 4 weeks	Study Visit 1 (Enrollment/Baseline) Week 1 +/- 2 weeks*
Screening Questionnaire	X	
Review Medical Records	X	
Demographics	X	
Informed consent		X
History and Physical Exam, Cardiology Evaluation		X
Concomitant medication review		X
Vital signs		X
ECG, Echo, PFT, Chest CT, Neuromuscular Ultrasound		X
Biospecimen Collection (blood and urine) ^a		X
Physical Assessment (6MWT, SPPB/Mini-BEST, CPET)		X
VAS-CFS and Qualitative interviews ^b		X
Patient-reported Outcomes and QOL		X
Physical activity and sleep quality monitoring		X
Other assessments (e.g. neurology, vascular function)		X
Optional assessments (brain MRI, skin biopsies)		X
Randomization		X
Adverse event review and evaluation		X
Complete Case Report Forms (CRFs)		X
^a Including urine pregnancy test (women of childbearing potential); ^b Repeated before and up to 72 hours after the CPET		
*May extend to 30 days from enrollment		

Abbreviated Title: Exercise and COVID-19
Version Date: 3/18/2025

Continued: SOA for AET+ group

	Intervention Period 1 Week 3 +/- 1 week	Study Visit 2 (10-week follow-up) Week 14 +/- 4 weeks	3-month follow-up 1 Week 30 +/- 1 week	3-month follow-up 2 Week 43 +/- 1 week	3-month follow-up 3 Week 56 +/- 1 week	3-month follow-up 4 Week 69 +/- 1 week
Procedures						
History and Physical Exam, Cardiology Evaluation		X				
Concomitant medication review		X				
Vital signs	X	X				
ECG, Echo, PFT, Chest CT, Neuromuscular Ultrasound		X				
Biospecimen Collection (blood and urine) ^a		X				
Physical Assessment (6MWT, SPPB/Mini-BEST, CPET)		X				
VAS-CFS and Qualitative interviews ^b		X				
Patient-reported Outcomes and QOL		X	X	X	X	X
Physical activity and sleep quality monitoring	X	X	X	X	X	X
Other assessments (e.g. neurology, vascular function)		X				
Optional assessments (skin biopsies)		X				
Supervised Exercise Session (thrice weekly)	X					
Education Sessions (weekly)	X					
Adverse event review and evaluation	X-----					X
Complete Case Report Forms (CRFs)	X-----					X
^a Including urine pregnancy test (women of childbearing potential); ^b Repeated before and up to 72 hours after the CPET						

Abbreviated Title: Exercise and COVID-19
Version Date: 3/18/2025

Continued: SOA for CON group

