5.6 STRATEGIES FOR RECRUITMENT AND RETENTION

- The target number of enrolled adults aged 18 to 80 years is 76. There are no limits related to gender, race or ethnicity. It is anticipated that up to 90 participants will be required to attain the target enrollment.
- The recruitment rate is expected to be 4 – 8 persons each month
- Participants will be primarily recruited from the greater Washington DC capital area
- Recruitment of participants from other NIH studies may also occur (e.g., 20-CC-0113: Cardiopulmonary Inflammation and Multi-System Imaging During the Clinical Course of COVID-19 Infection in Asymptomatic and Symptomatic Persons, 18-H-0011: Technical Development of Cardiovascular Magnetic Resonance Imaging (CMR) Using a Low Specific Absorption Rate (SAR) Scanner System; 14-H-0188: Prospective Evaluation of Next Generation CT Reconstruction, 000089-N: Natural History of Post-Coronavirus Disease 19 Convalescence at the National Institutes of Health)
- Direct patient referrals from physicians and clinics in the greater Washington DC capital area such as Inova Fairfax Hospital, Suburban Hospital, etc.
- The recruitment strategy offered by the NIH/CC Office of Patient Recruitment, including sample recruitment messages and advertisements in the form of study flyers will be used. IRB-approved flyers may be left with clinics for interested treating physicians to refer participants to this study with approval of the venue or in accord with their policy; self-referral is also permitted. Study flyers and physician letters may be sent using commercially available mailing lists via direct mail. Recruitment flyers may also be given directly or sent electronically to those requesting study information. Flyers may be made available at outreach exhibits, speaking engagements, support group meetings, professional meetings or association/trade meetings with approval of the venue or in accord with their policy.
- IRB approved flyers may also be posted in the community at venues such as grocery stores, community centers, universities, bookstores and libraries or placed in possible venues such as advocacy group offices, in doctor's office waiting rooms, places of worship, public libraries and retail establishments with approval of the venue or in accord with their policy.

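### The 90 participants stated in section 9.2 are not what its own closing rule delivers: taken literally, the rule gives about 103 to 107 randomised

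*Combined protocol and SAP*

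**What the plan says.** Section 9.2 sets 38 per group for 80% power, expects 85% of randomised participants to complete Visit 2, and concludes that 90 people "need to be randomized in order to achieve 76 completed participants". The next sentence gives the closing rule: "Recruitment will remain open until 38 participants in each of the AET+ and CON cohorts have completed at least the second study visit". Accrual is put at "approximately 4 to 8 participants will be enrolled each month", and the same sentence expects the enrolment target to be reached in 1.5 to 2 years.

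The number 90 appears in two other places. The synopsis (1.1) describes the study population as "Ninety male and female adults (18 to 80 years old) recovering from COVID-19". Section 5.6 sets a target of 76 enrolled and adds: "It is anticipated that up to 90 participants will be required to attain the target enrollment".

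The schedule of activities (1.3) puts Visit 1 and randomisation at week 1, and the primary time point at "Study Visit 2 (10-week follow-up) Week 14 +/- 4 weeks". Section 7.2 says that participants who receive the intervention and later withdraw are to be replaced. No section says whether 90 is a ceiling or an expectation, or when the primary dataset is closed.

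**The concern.** The two statements in 9.2 count different things. Dividing 76 by 0.85 gives the number of people whose Visit 2 outcome must be known, as completed or lost. The closing rule counts completed visits as they occur, and a completed Visit 2 trails randomisation by about three months. People randomised in that interval are in the trial but not in the count. The rule also needs 38 in each arm, so the slower arm sets the date.

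What is at stake is the size of the trial. The number shown to those approving a protocol classed as more than minimal risk, with maximal exercise tests and possible repeat chest CT, should be the number its rule produces. The point at which recruitment closes, and the final number to be followed, should also be clear in advance.

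**Working it through.** **Inputs.** From 9.2: difference 56.7 m, SDs 98.6 and 71.3 m, alpha 0.05 (two-sided assumed, as sidedness is not stated), 80% power, 38 completers per arm, 85% completion, 4 to 8 enrolled per month, 1.5 to 2 years. From 1.3: Visit 1 at week 1; Visit 2 at week 14 with a window of 4 weeks either side, so a lag of 13 weeks (9 to 17). From 6.2: 1:1 allocation in blocks of 4 and 6.

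**1. The plan's own figures.** Welch t-test power is 79.8% with 37 per arm and 80.8% with 38, so 38 reproduces. 76 / 0.85 = 89.4, rounded up to 90, or 45 per arm.

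**2. Accrual rate.** 90 people over 24 to 18 months is 90/24 = 3.75 to 90/18 = 5.0 per month. A sustained 8 per month would reach 90 in 90/8 = 11.25 months, which does not fit the stated timeline.

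**3. Number needed before both arms yield 38 completers.** Simulation with blocks of 4 and 6 and 85% completion gives a mean of 92 (5th to 95th percentile about 85 to 101). It exceeds 89.4 because both arms must reach 38.

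**4. Entrants during the lag.** Pipeline = monthly rate x lag in months. Thirteen weeks = 13 x 7 / 30.44 = 2.99 months; 9 weeks = 2.07; 10 weeks = 2.30.

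| Lag | Rate per month | Pipeline | Total randomised (92 + pipeline) | Awaiting Visit 2 |
|---|---|---|---|---|
| 13 weeks | 3.75 | 11.2 | about 103 | 11% |
| 13 weeks | 5 | 14.9 | about 107 | 14% |
| 13 weeks | 4 | 12.0 | about 104 | 11% to 12% |
| 13 weeks | 8 | 23.9 | about 116 | 21% |
| 10 weeks | 3.75 to 5 | 8.6 to 11.5 | about 101 to 104 | 9% to 11% |
| 9 weeks | 4 to 8 | 8.3 to 16.6 | about 100 to 109 | 8% to 15% |

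If the 1.5 to 2 years refers to the 76 in section 5.6, the rate is 76/24 = 3.2 to 76/18 = 4.2 per month. The 13-week total is then about 102 to 105.

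**5. State of the count at 90.** With a 13-week lag and random arrivals at 3.75 to 5 per month, about 63 to 66 people have completed Visit 2 when the 90th is randomised. The rule therefore says to continue. Even at 2 per month with a 9-week lag, the total passes 90 in about 86% of simulated trials.

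**6. If 90 is a cap.** With 45 per arm, the chance that one arm has at least 38 completers is P(Bin(45, 0.85) >= 38) = 0.639. For both arms it is 0.639 squared = 0.41. Expected completers are 45 x 0.85 = 38.25 per arm. Averaged over the binomial spread of completers, Welch power is about 81%.

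**The case against.** The arithmetic in 9.2 is correct as far as it goes: 38, 76 and 90 all reproduce. Section 5.6 speaks of up to 90, which can be read as a ceiling, and the rule may simply guarantee a floor of 38 per arm, in keeping with the replacement provision in 7.2. All of that is fair. It does not reconcile the two statements, because under a ceiling of 90 the floor is met only about 41% of the time.

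Four stronger readings are tempting, and the documents do not support them.

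- **That about 116 would be randomised, with 21% pending.** This needs a sustained 8 per month, which conflicts with the 1.5 to 2 years given in the same sentence. It is an upper case.
- **That those pending cannot have reached the primary time point.** Thirteen weeks is nominal. The window opens at week 10, and 9.2 and 9.4.2 both describe a 10-week time point.
- **That late entrants are left out of the analysis or power is lost.** The rule closes recruitment. No section makes it a data cut-off, no interim analysis is planned (9.4.6), and 9.3 defines the analysis set by exercise attendance, not by date of entry. Extra completers would raise power.
- **That the sample size is settled after outcomes are seen.** The trigger is a count of completed visits and does not use walk distances.

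One further reservation stands. The accrual rate is for people enrolled, and some are excluded after consent (for example on the baseline 6MWT), so the randomisation rate and the overshoot may be smaller.

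**Conclusion.** The point holds as an internal inconsistency in the stated sample size. Followed literally, the closing rule overshoots 90 by about 13 to 17 people (103 to 107) on the plan's own timeline, and by about 10 to 26 (100 to 116) across 4 to 8 per month and a lag of 9 to 13 weeks. This rests on 85% completion in each arm, steady accrual, and enrolled people being randomised at the stated rate. The direction is robust to a much slower rate; the size is not. It is worth correcting because the correction is cheap and the number of participants is a figure that others rely on. It does not threaten the validity or the power of the primary comparison.

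**What to change.** In 9.2, adopt one of two wordings.

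- **(a) Close on a number randomised.** Randomisation ends at 90 (about 45 per arm), and the primary analysis waits until the last of them has passed the Visit 2 window. State the downside openly: about a 41% chance that both arms reach 38 completers, with average power still about 81%.
- **(b) Keep the completer rule.** Restate the expected number randomised as about 103 to 107 (up to about 116 at 8 per month). Say that everyone already randomised at closure is followed to Visit 2 and is eligible for the analysis.

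Under either wording, make 1.1 and 5.6 agree and say whether 90 is a cap. Also state how the replacement rule in 7.2 counts towards the total, since replacing withdrawn participants on top of a fixed 90 would reopen the problem.

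The cost is wording in four sections. Option (a) probably means fewer participants but gives up the guarantee of 38 per arm. Option (b) keeps that guarantee but needs approval for the larger number. Neither option should be used to alter the per-protocol population in 9.3, which is a separate matter.
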